Pharmacological support includes; NSAIDS, opioids, or sedation and analgesia medications (while intubated). Among these medications, lidocaine has recently been emerging as a superior method of choice.⁵ Recent evidence-based literature (randomized controlled trials [RCTs], systematic reviews, Cochrane review, and expert opinion) has shown that lidocaine as an intracuff media for patients who are mechanically ventilated, can reduce sedative requirements thereby improving ETT tolerance, and can reduce EP.⁵⁻⁸ Reducing sedation may result in: less side effects of the sedation medication, a quicker extubation time leading to a shorter stay in the ICU, and a reduction in overall cost.

The proposed study seeks to investigate the efficacy of instillation of buffered lidocaine as an endotracheal tube cuff medium on post-operative sedative requirements, time to extubation, and frequency of emergence phenomena in a population of adult patients undergoing cardiac surgical procedures requiring endotracheal intubation.

After completion of a thorough review of the current literature, the optimal route for investigating the above clinical question is a prospective feasibility study to determine the effect of 1.8% lidocaine/0.76% sodium bicarbonate in the ETT cuff for the stated outcomes. The proposed research project will be called, the lidocaine project and will be conducted in the cardiac surgery ICU at Saint Mary's Hospital (Mayo Clinic), in Rochester, MN. This setting is highly desired due to the high volume of cardiac surgeries being performed at Mayo Clinic. This population of patients proves to be consistent in their post-operative recovery period and quite often is extubated within 6 hours. This will provide a substantial window of opportunity to study the effects of the intervention.

References

2. Basuni A. Intracuff alkalized lidocaine reduces sedative/analgesic requirements for mechanically ventilated patients. *Saudi J. Anaesth.* 01 Oct 2014;8(4):451-455.
3. Scuderi PE. Postoperative sore throat: more answers than questions. *Anesth. Analg.* 2010;111(4):831-832.

- Cardiac surgery includes: single valve repair, myectomy, CABG, pericardectomy.
- Patients who are anticipated to be deemed, "rapid recovery," in the cardiac surgery ICU at St. Mary's Hospital
-

Exclusion Criteria:

- Age < 18 years old at time of surgery
- Patients who cannot consent themselves or non-English speaking patients who require an interpreter
- Patients who are not sent to the cardiac ICU post-operatively
- Patients who are anticipated to have a difficult tracheal intubation
- Patients having risk factors of postoperative aspiration of gastric contents
- Patients who have respiratory disease or recent respiratory tract infection
- > 2 attempts to secure an airway
- Patients undergoing TAVR procedures or any form of "robotic," procedures

Methods:

Patients will be chosen based on their inclusion/exclusion criteria. Patients during their clinic appointment prior to surgery were provided a thorough explanation of the intervention and study, if the patient agrees to participate; he or she will be included in the study. The day of the procedure, the patient will have the intervention take place while in the operating room by the Registered Respiratory

Therapist (RRT), Certified Registered Nurse Anesthetist (CRNA) or Anesthesiologist. The patient will remain intubated after the surgery is complete and will be taken to the cardiac surgical ICU.

At the induction of anesthesia, patients will be breathing 100% oxygen via a face mask and then, become anesthetized according to a standard protocol and at the discretion of the attending anesthesiologist. Patients will be receiving fentanyl, lidocaine (as an IV anesthetic preventing uncomfortable side effect Propofol can create in the arm) and either succinylcholine or vecuronium to facilitate tracheal intubation. Laryngoscopy will then be performed and the trachea intubated with a standard cuffed ETT. ETT tubes from 6.0mm to 8.0mm in diameter will be used. Inflation of the ETT cuff will be performed in accordance with the randomization of either air or 1.8% lidocaine/0.76% solution until such time as there is no air leak around the tube when administering positive pressure to 20 cm H₂O. Checking for intermittent leaks to ensure a minimum seal is present will be done as needed per standard of care. Anesthesia will be maintained with volatile anesthetic with or without a Propofol infusion. Vecuronium will be used to maintain the ulnar nerve train-of-four at 0–3 of four twitches. Anesthesia maintenance will occur until the near end of the surgical procedure. The volatile anesthetic will be discontinued and Propofol will be initiated via a continuous infusion to facilitate transportation to the intensive care unit (ICU). After arrival to the ICU, Neuromuscular blockade will then be antagonized with suggamadex reversal agent, and the pharynx being gently suctioned under direct vision. Mechanical ventilation to be maintained until swallowing or spontaneous respiration begins, and then, converted to assisted manual ventilation. Extubation will be performed at ICU provider's discretion once the extubation protocol criteria are met.

The patient then will be closely monitored as a 1:1 by the room nurse, and by other staff (respiratory therapist, and ICU fellows and consultants) for toleration of the ventilator (coughing, double triggering, "bucking," etc.) on the cardiac surgical intensive care unit. Sedation amount will be recorded electronically from initiation of the mechanical ventilation weaning protocol until the time of extubation. The RRT will physically record "yes," or "no," on the form provided regarding the patient coughing, complaining of a sore throat or difficulty swallowing, having hoarseness or difficulty speaking.

Sample Size:

The sample size for this investigation is determined for the primary endpoint of total propofol dose in the first 4 hours. Basuni (2014) reported differences in propofol dose of approximately 0.7 SD for patients receiving saline vs lidocaine+bicarb.

The current investigation is considered a randomized Phase II study, with the objective of determining whether or not additional studies of the current treatment intervention are warranted. Although debate exists regarding the value of formal statistical comparisons in phase II trials, we agree with those who propose that a one-sided test with a false-positive (type I error) rate of 0.10 for the primary endpoint is an appropriate criterion to use to help guide the decision-making process. In general, a sample-size of N=20 patients per group will provide statistical power (one-tailed, alpha=0.10) of 80% to detect a difference between groups of 0.7 standard deviation units.

Data Collection:

Regarding the primary outcome, total sedation required from the time of the patient entering the ICU until extubation, will be recorded in the electronic charting documentation.

Regarding a secondary outcome, the total amount of time the patient is intubated (from the time they enter their room in the ICU from surgery) will be recorded by the RRT on the assessment form provided.

Regarding the secondary outcomes, patient assessment forms will be provided in the envelopes (attached to patients chart) for the study team, SRNA, to fill out. Completed assessments will be collected at the end of each day and will be manually analyzed at the end of the study once the sample size is reached.

Data Analysis

Data will be summarized using mean \pm SD, or median [25th, 75th] for continuous variables and frequency counts and percentages for nominal variables. The primary endpoint will be sedative dose (Propofol, precede, fentanyl, ketamine) amount from the mechanical ventilation weaning protocol initiation until ETT extubation. This endpoint will be compared across groups using the two-sample t-test, or rank sum test. Secondary endpoints will include; time to extubation (from initiation of the mechanical ventilation weaning protocol); and coughing, restlessness, hoarseness, and dysphagia. Sedative dose will be treated as continuous variables and analyzed using ANOVA. Post-extubation endpoints will be dichotomized and analyzed using logistic regression. In all cases, distributional assumptions will be assessed with transformations or nonparametric methods used as appropriate.

Statistical Analysis:

Recorded characteristics will be presented using mean \pm SD or median (IQR) for continuous variables and frequency percentages for categorical variables. Summaries of these variables will be presented overall. The primary outcome will be compared using analysis of variance (ANOVA). Secondary analyses will also be performed and analyzed using logistic regression. Two-tailed p-values ≤ 0.05 will be considered statistically significant in all analyses.

Strengths

Despite variation in co-morbidities and surgery types, all patients deemed rapid recovery eligible have necessarily undergone screening for complications, hemodynamic stability, adequacy of hemostasis, and anticipated readiness for extubation within 2 to 6 hours. This improves the generalizability of study results. All patients have the added benefit of being closely and safely monitored by the cardiac ICU team during the entire duration of the intervention. There will be a pharmacist on the ICU as well to help with any discrepancies that may arise. The study is using a sample size with sufficient enough power to gain a greater separation of results between the control and intervention arms.

Limitations

Our team acknowledges several limitations. Only a single lidocaine concentration and a single sodium bicarbonate concentration will be studied. Previous studies have compared various concentrations of sodium bicarbonate; results have not shown a difference in patient outcomes. Future projects could investigate other instillation solutions to further optimize therapeutic efficacy. There is data that the heart rate can be lower in patients receiving alkalinized lidocaine. However it is common for postoperative cardiac surgical patients to have paced rhythms and vasoactive drug infusions, both of which can derange the HR. HR will not be included as a secondary outcome, however could be something to consider in future studies. Oxygen saturation proves difficult to record as many factors can give a false reading (transient face mask, turning up of nasal cannula not often charted), so this was left out as a potential secondary outcome. Hypercarbia could be included in future studies as a secondary outcome. This study left it out because it requires ensuring that a post-extubation arterial blood gas is obtained. This quite often is not reliably obtained nor is the time to obtain the sample standardized. Future research regarding the use of lidocaine as an ETT cuff media could certainly entertain the idea of incorporating some of these potentially important outcomes.

Budget

After first obtaining IRB approval, funding will be applied for through the Mayo Clinic Center for Clinical and Translational Science (CCaTS) 2017 Small Grants Program (SGP) allocation for the Department of Anesthesiology. CCaTS Research Resources will assist with the statistical analysis.

Should a poster be generated to disseminate results, under the new institutional guidelines for poster development and preparation, Media Support Services will provide support and print the poster at no charge.

Human Subjects

Description

This study will be conducted as a feasibility study prospectively comparing a single group of patients receiving lidocaine, respectively via the ETT cuff.

Research Materials:

No biological specimens will be obtained.

Confidentiality and Data Management

The confidentiality of all study participants will be maintained. After the outcome measures are collected, data will be abstracted and entered into an electronic database. At the time of data entry, all personal identifiers will be removed. When not in use, the electronic database will be securely housed in the administrative offices of the Anesthesia Clinical Research Unit.

Informed Consent

Written informed consent will be obtained from all study participants prior to involvement in the study protocol. All potential study subjects will be told that declining to participate in the research project will in no way impact their medical care at Mayo Clinic.

Potential Risks:

There is an extremely rare chance the ETT cuff could rupture. There has been a recent documented incidence however, involving a patient who received an unknown amount of lidocaine in their ETT during a non-study, off-label use of lidocaine. The patient did have a negative outcome regarding vocal cord injury, although it should be known that this could have occurred due to a variety of reasons ranging from improper ETT placement, coughing, cuff/tube migration, pain/light anesthetic agent, etc. In case of ETT cuff rupture, and to avoid potential systemic toxicity, we will be using a dose which is well under the toxic level, as documented by previous literature. Other potential risks are none greater that would otherwise normally occur to a typical cardiac surgery ICU patient.

In addition, the potential risks that have been investigated in the literature for this topic are comprised of: two meta-analyses, many randomized-controlled trials, and one retrospective case-control study. The majority of this evidence is level II, with two level I meta-analysis on the Ackley level of evidence scoring tool, indicating a high level of quality, reliability, and generalizability, with a low risk of bias among the evidence.¹ For over 20 years, researchers have been experimenting with lidocaine to help patients overcome the various side effects and complications of being intubated. There have been a few studies conducted to determine the safety and efficacy of lidocaine diffusion across the polyurethane cuff of the endotracheal tube.^{2,3} Both Estebe et al.⁴ and Huang et al.³ determined that alkalinization of lidocaine is safe to use, without compromising the integrity of the cuff and improves the diffusion when compared to lidocaine alone. Since these studies, most researchers have utilized alkalinized lidocaine in intracuff studies, and there have even been a few studies that have compared different concentrations of lidocaine.^{4,5} This high level of evidence will guide a protocol for the

anesthesia and intensive care staff at Mayo Clinic caring for rapid recovery cardiac surgery patients. This study will improve and elaborate on the science behind intracuff lidocaine and the positive impact on lowering patient sedation requirements, as well as, bridge the gap between current studies with endotracheal lidocaine and decreased sedation in the intensive care setting. While reviewing the literature, there were no reported cases of sentinel events or tube rupture.

With the scientific evidence, our team has also consulted with multidisciplinary groups across the campus to ensure safety and efficacy of this study. The critical care respiratory therapists group has been educated on the science behind this study, and their role in protecting the patient's airway. The respiratory therapists will continue to do all of their normal safety assessments, in addition to monitoring how much lidocaine is in the cuff upon arrival to the ICU and at extubation to ensure there is not over or under inflation. The team has also obtained approval from the Critical Care Service consultant group. This group of highly experienced physicians was briefed on the exact procedures that will take place throughout this study, including the benefits and potential risks.

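### The trial is powered on propofol dose alone, but the primary endpoint to be analysed is a four-drug sedative amount with no unit or combination rule

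*Combined protocol and SAP*

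**What the plan says.** Three sections describe the primary endpoint, and they do not describe the same variable.

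- **Sample Size:** "The sample size for this investigation is determined for the primary endpoint of total propofol dose in the first 4 hours". The effect size comes from a cited study that "reported differences in propofol dose of approximately 0.7 SD for patients receiving saline vs lidocaine+bicarb". The criterion is "a one-sided test with a false-positive (type I error) rate of 0.10 for the primary endpoint", and "a sample-size of N=20 patients per group will provide statistical power (one-tailed, alpha=0.10) of 80" per cent for a difference of 0.7 SD.
- **Data Collection:** the primary outcome is "total sedation required from the time of the patient entering the ICU until extubation". No drug is named.
- **Data Analysis:** "The primary endpoint will be sedative dose (Propofol, precede, fentanyl, ketamine) amount", measured "from the mechanical ventilation weaning protocol initiation until ETT extubation". The next sentence compares this endpoint, in the singular, between groups by t-test or rank sum test. Later in the same paragraph, sedative dose is said to be analysed by ANOVA as continuous variables, in the plural.

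No section gives a unit for the amount, a conversion to a common scale, a weighting, or a rule for combining the four drugs. No section gives an SD or an effect size for anything but propofol.

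**The concern.** Two things follow from reading these sections together.

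First, the power statement belongs to a different variable from the one to be tested. The trial exists to decide whether further studies are warranted, and that decision rests on the primary comparison.

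Second, the analysed endpoint cannot be computed as written. From the same charts, one analyst could sum masses, another could use propofol only, a third could apply an equivalence, and a fourth could run one test per drug. The choice would be made with the data in hand.

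The choice also matters in substance. If masses are added, a drug given in micrograms hardly registers beside one given in hundreds of milligrams. A patient moved from propofol to such a drug would score as little sedated. The plan describes no blinding of ICU staff, and under Potential Risks the respiratory therapists check how much lidocaine is in the cuff on arrival. A difference between arms in changes of agent therefore cannot be ruled out. If there were one, it would appear as a treatment effect.

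**Working it through.** **1. Reproduce the plan's figure.** Inputs from Sample Size: d = 0.7 SD, 20 per group, one-sided alpha 0.10, power 80%.

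- Normal approximation: n per group = 2 × (1.2816 + 0.8416)² / 0.7² = 9.016 / 0.49 = 18.4, so 19.
- Power of the t-test at 20 per group: 38 degrees of freedom, noncentrality 0.7 × √(20/2) = 2.214, giving 81.8%.

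The stated 20 per group at 80% reproduces. The calculation is not wrong; it applies to propofol dose.

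**2. Reading A: the four amounts are summed by mass.** The word precede is taken here to mean dexmedetomidine. The infusion rates below are assumptions for scale only, since the documents give none: 80 kg, 4 hours, propofol 10–50 mcg/kg/min, dexmedetomidine 0.2–0.7 mcg/kg/h.

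- Propofol: 0.010 to 0.050 mg/kg/min × 80 kg × 240 min = 192 to 960 mg.
- Dexmedetomidine: 0.2 to 0.7 mcg/kg/h × 80 kg × 4 h = 64 to 224 mcg = 0.064 to 0.224 mg.
- Largest share of the sum: 0.224 / (192 + 0.224) = 0.12%. Smallest: 0.064 / (960 + 0.064) = 0.007%.

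Effect of a change of agent halfway through, taking the lowest propofol and highest dexmedetomidine rates: 96 mg + 0.112 mg = 96.1 mg, against 192 mg for a patient kept on propofol. The endpoint records a 50% reduction, although the patient was sedated throughout.

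**3. Reading B: each drug is tested separately.** There are then four primary tests. At one-sided 0.10 each, the chance of at least one false positive is 1 − 0.90⁴ = 34% if the tests are independent. It is 10% if they are perfectly correlated and at most 4 × 10% = 40% in general. No lead drug and no multiplicity rule is given, and only propofol has an effect size behind it.

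**4. Can the power be carried over to a four-drug amount?** Let r be the SD of the non-propofol part divided by the SD of the propofol part, on whatever scale is used. Assume that the two parts are uncorrelated and that treatment acts on propofol only. The effect becomes 0.7 / √(1 + r²).

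| r | Effect (SD) | Power, 20 per group, one-sided 0.10 (t-test) | n per group for 80% (normal approx.) |
|---|---|---|---|
| 0 | 0.70 | 82% | 19 |
| 0.25 | 0.68 | 80% | 20 |
| 0.5 | 0.63 | 75% | 23 |
| 1.0 | 0.49 | 60% | 37 |
| 1.5 | 0.39 | 47% | 60 |

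The documents give no value of r. For dexmedetomidine in a mass sum it is negligible: with SDs of about 0.2 mg and 77 mg (40% of 192 mg, an assumption), r = 0.2 / 77 = 0.003 and the effect stays at 0.70. Fentanyl and ketamine were not worked out. If the other drugs also fall with treatment, the loss shrinks or reverses.

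**The case against.** The plan never says the amounts are summed. The plural in Data Analysis could mean one analysis per drug, and the Methods name only propofol as the infusion started for transfer to the ICU. This is a small feasibility study, and rank tests and transformations are allowed.

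Much of that stands. Summing is the natural reading of a single endpoint with a single test, but it is not stated. Drug-by-drug testing does not rescue the plan, however; it replaces an undefined sum with four uncontrolled tests. A rank test or transformation supplies no common unit, because it ranks or transforms whatever total was built. No frequency of changing agent is given, so bias between arms is possible but not shown.

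A reader might also infer three stronger things that the documents do not support:

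- *That pooling adds noise and so cuts power by a known amount.* For dexmedetomidine the small share works the other way: a mass sum is almost propofol alone, and its power barely moves. For that drug the problem is substitution.
- *That dose is analysed in raw milligrams.* The documents state no unit.
- *That body-weight variation dilutes the 0.7 SD.* This requires the cited effect to have been per kilogram. The Sample Size section says only propofol dose. If the cited SD was in milligrams, weight variation is already in it.

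**Conclusion.** The powered and analysed primary endpoints differ, and the analysed one has no unit or combination rule. This should be settled before analysis, because the primary result is otherwise undefined.

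The mismatch in drugs and the missing rule rest on the text alone. The 80% power figure (81.8% on recalculation) is supported for propofol only. It should not be read as a sample-size error, nor as proof that the trial is underpowered: the 47% to 82% range depends on an assumed variance ratio and on treatment acting on propofol alone. The dexmedetomidine share of about 0.1% depends on assumed infusion rates and on summing by mass.

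Two related discrepancies are separate points, but touch the same sentences: the measurement window differs between sections, and the test level for the same endpoint is one-sided 0.10 in Sample Size, whereas Statistical Analysis says "Two-tailed p-values ≤ 0.05 will be considered statistically significant in all analyses". At that second level, 20 per group gives about 58% power for 0.7 SD.

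**What to change.** State one primary endpoint, in the same words, in Methods, Sample Size, Data Collection, Data Analysis and Statistical Analysis.

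**Cheapest choice: total propofol dose.** It is the only endpoint with a cited effect size.

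- Give one measurement window, and use the unit on which the 0.7 SD was based, checked against the cited study.
- Report each other agent by arm as secondary: any use, and total in its own unit.
- Add a sensitivity analysis in which patients who received another sedative in the window are ranked worst (highest sedation), compared by rank sum test. Placing them only above patients with the same propofol dose is not enough, because a patient switched early would still rank below those kept on propofol. List in advance which agents trigger this rank; if one is given to nearly everyone, the analysis says little.

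**Alternative: a composite.** Prespecify a referenced conversion of all four drugs to one scale, with an SD and effect for that composite, and restate the power at the chosen test level.

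The first option costs wording and one extra analysis, since the plan already records sedation electronically. Its downside is that the headline result covers propofol only, which is narrower than the sedation requirements of Aim 1; the by-arm report of other agents partly offsets this. The composite stays closer to Aim 1, but needs a defensible conversion and possibly a new sample size.

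### Ordinary logistic regression on yes/no symptoms with 20 patients per arm gives no usable odds ratio, interval or Wald p-value when one arm has no events, and the plan names no alternative

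*Combined protocol and SAP*

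**What the plan says.** The Data Analysis section lists coughing, restlessness, hoarseness and dysphagia as secondary endpoints and states: "Post-extubation endpoints will be dichotomized and analyzed using logistic regression". The Statistical Analysis section adds only "Secondary analyses will also be performed and analyzed using logistic regression" and sets the criterion "Two-tailed p-values ≤ 0.05 will be considered statistically significant in all analyses".

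The Sample Size section plans "a sample-size of N=20 patients per group", sized on the primary sedative endpoint alone. No expected symptom rate is given for either arm.

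The plan does not say whether the logistic p-value is Wald or likelihood-ratio. It names no exact or penalised method and no rule for an arm with no events. The nearest safeguard is a general clause: "In all cases, distributional assumptions will be assessed with transformations or nonparametric methods used as appropriate". Nominal variables will also be summarised as counts and percentages.

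**The concern.** If lidocaine works as hoped, a symptom that is uncommon to begin with may occur in none of the 20 treated patients. The fitted log odds ratio then runs off to minus infinity, and its standard error grows without limit. The coefficient table that most software prints shows a p-value near 1. The same happens if every patient in an arm has the symptom.

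The result is perverse: going from one event to none in the lidocaine arm can turn a significant finding into p near 1. At stake are the odds ratio, its interval and possibly the significance verdict for one or more symptoms. A second issue is that the usable tests can disagree on such data, so an unnamed test leaves the choice to be made after the counts are known.

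**Working it through.** **Inputs.** From the documents: 20 per arm (Sample Size), logistic regression (Data Analysis), two-sided 0.05 (Statistical Analysis). Assumed, because the documents give none: symptom rates from 2% to 70%. The model contains treatment only, as the plan names no covariates.

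**The plan's own figure.** The stated power is 80% for 0.7 SD at one-sided 0.10. The noncentral t distribution with 38 degrees of freedom gives 81.8%, so the figure reproduces. It concerns the primary endpoint and says nothing about the symptoms.

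**Step 1: one table, control 6/20 versus lidocaine 0/20.**
- Wald: the log odds ratio is not finite. Software stops at an arbitrary large value (here about -25, standard error about 53,000), giving p = 0.9996.
- Likelihood ratio: the fitted log-likelihood is 6 ln 0.30 + 14 ln 0.70 = -12.217. Under no effect it is 6 ln 0.15 + 34 ln 0.85 = -16.908. Twice the difference is 9.38 on 1 df, so p = 0.002.
- Fisher: 2 × C(20,6)/C(40,6) = 2 × 38,760/3,838,380 = 0.020.
- Firth: in a 2×2 table this adds one half to each cell. The odds ratio is (0.5/20.5)/(6.5/14.5) = 0.054, with penalised likelihood-ratio p = 0.008.

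**Step 2: other tables.**

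| Control vs lidocaine | Wald | Likelihood ratio | Fisher | Firth |
|---|---|---|---|---|
| 2/20 vs 0/20 | 0.9997 | 0.090 | 0.49 | 0.21 |
| 4/20 vs 0/20 | 0.9996 | 0.014 | 0.106 | 0.043 |
| 10/20 vs 0/20 | 0.9996 | 0.00003 | 0.0004 | 0.0001 |
| 10/20 vs 1/20 | 0.009 | 0.0007 | 0.003 | 0.001 |

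A single event restores the Wald test. At 4/20 versus 0/20 the verdict depends entirely on which test is used.

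**Step 3: how often an arm is empty.** P(0/20) = (1 - p)^20.

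| Assumed true rate | 2% | 5% | 10% | 15% | 20% | 30% |
|---|---|---|---|---|---|---|
| P(0/20) | 67% | 36% | 12% | 4% | 1% | under 0.1% |

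By symmetry the same figures apply to 20/20 at rates of 98%, 95%, 90% and so on.

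**Step 4: power at two-sided 0.05.** All 21 × 21 possible tables were enumerated with their binomial probabilities, counting Wald as non-significant when an arm has 0 or 20 events.
- 40% vs 5%: Wald 42%, Fisher 72%, likelihood ratio 82%, Firth 82%.
- 30% vs 2%: Wald 12%, Fisher 62%, likelihood ratio 82%.
- 50% vs 20%: Wald 48%, Fisher 41%, Firth 49%.
- 60% vs 25%: Wald 58%, Fisher 49%.
- 70% vs 30%: Wald 70%, Fisher 60%.

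**Step 5: type I error (nominal 5%), same enumeration with equal rates.** At 10% vs 10%, likelihood ratio 8.5% and Fisher 1.2%. At 50% vs 50%, Fisher about 2%. Firth stayed below 5% at every null rate checked from 5% to 50%.

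**The case against.** A reader might infer that the plan would report the strongest possible benefit as p close to 1. The documents do not support that, for four reasons.

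- **The Wald test is never named.** The likelihood-ratio p-value comes from the same ordinary model and does not collapse. This stands. It does not rescue the odds ratio or the Wald interval, and its type I error is inflated for rare symptoms.
- **The fallback clause could admit an exact test.** This stands in part. The clause is triggered by distributional assumptions, and separation is not clearly one of those. It names no method or trigger, so any choice would follow sight of the data.
- **An empty arm is not always strong evidence.** At 2/20 versus 0/20 no test in the table above is significant. This stands.
- **The result would be visible.** Counts and percentages would show 0/20, and a huge standard error is hard to overlook. This stands, but the plan's significance criterion is still a p-value.

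It is also fair to say that the symptoms are secondary endpoints in a small feasibility study, and that the decision criterion in the Sample Size section rests on the sedative endpoint, which is untouched.

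Finally, the obvious remedy of using Fisher's test throughout is not free. At common rates, where empty arms hardly occur, it has 7 to 10 points less power than Wald in the scenarios above.

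**Conclusion.** The point holds as a gap in pre-specification. With 20 per arm, the only method named for the symptoms cannot give a finite odds ratio or usable Wald interval when an arm has 0 or 20 events, and its default p-value is then uninformative. No clear rule covers that case.

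The size rests on assumed rates. If a symptom's true rate in an arm is about 10% or lower (or, symmetrically, 90% or higher), the chance of this is 12% or more. At 20% it is about 1%, and at 30% it is negligible. If Wald output is used, the power loss at 40% versus 5% is 40 points against Firth (42% versus 82%). At 50% versus 20% it is one point.

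Only secondary endpoints are affected. This is a cheap improvement and not a threat to the trial's main conclusion.

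**What to change.** In the Data Analysis section, replace the sentence on post-extubation endpoints with:

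> Each dichotomised symptom is analysed by Firth-penalised logistic regression with a penalised likelihood-ratio p-value and profile-likelihood 95% interval, and the risk difference is reported with a Newcombe 95% interval.

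Make the logistic regression sentence in the Statistical Analysis section refer to it. Firth matched or beat Wald in power in every scenario run, held its type I error below 5%, and needs no switch of method after the data are seen.

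Do not replace logistic regression with Fisher's exact test for all symptoms, given the power it loses at common rates.

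The cost is slightly more analysis work and a less familiar estimator. No extra patients or data are needed.
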